#### 9.4.12 Concomitant Medications

Concomitant Medications will be documented using the Concomitant Medications form at Baseline and all study visits.

#### 9.4.13 Study Medication Adherence

Participants will be asked about his/her medication adherence at each appointment. Study personnel will count and record the number of pills in the patient's study medication bottles and provide immediate feedback, reinforcing the behaviors of patients who appear to be taking medications as prescribed and problem-solving with those who appear not to be. Clinicians will review with patients the use of pill-minder boxes, as needed.

#### 9.4.14 Laboratory Test Assessments

Northwestern Medicine Laboratory and South Bend Medical Foundation will be used for analysis of fasting lab assessments required during the study. Blood will be drawn from each patient at the screening visit, and at end of study as noted in the study Schedule of Events in Appendix 1. The tests will include: Chemistry panels; Hematologic parameters: red blood cell (RBC), hemoglobin, hematocrit, unconjugated bilirubin, reticulocyte, and platelet counts; Liver function: aspartate transaminase (AST), alanine transaminase (ALT), gamma glutamyltransferase (GGT), prothrombin time, total bilirubin, lactic dehydrogenase, albumin, protein, creatinine. A urine drug screen (UDS) will be obtained at screening only. In women of childbearing potential, serum pregnancy testing will occur at screening; urine pregnancy will occur at study baseline.

Note: At screening and throughout study participation, a positive UDS is not necessarily exclusionary and/or may not require a subject be withdrawn from the study. This decision will be per the discretion of the principal investigator.

#### 9.5 Safety Scales

#### 9.5.1 Abnormal Involuntary Movement Scale (AIMS)

The AIMS is a clinician-rated assessment of abnormal movements consisting of unobtrusive observation of the subject at rest (with shoes removed) and several questions or instructions directed toward the subject. Using a severity scale ranging from 0 (none) to 4 (severe), clinicians rate dyskinesia in several body regions, including the facial area, extremities, and trunk.

#### 9.5.2 Columbia Suicide Severity Rating Scale

The C-SSRS was developed by a team of researchers at Columbia University to address the need for standardized classification of suicide reports to assess suicide risk. This scale consists of a baseline evaluation that assesses the lifetime experience of the subject with suicide events and suicidal ideation and a post-baseline evaluation that focuses on suicidality since the last study visit. A baseline C-SSRS will be completed at the screening visit. The C-SSRS Since Last Visit form will be completed at all subsequent visits and telephone calls (Day 21, Day 35, and Day 49).

## 10.0 Data and Specimen Banking

Study documentation includes all Case Report Forms, data correction forms or queries, source documents, Janssen-Investigator correspondence, monitoring logs/letters, and regulatory documents (e.g., protocol and amendments, IRB correspondence and approval, signed patient consent forms).

Source documents include all recordings of observations or notations of clinical activities and all reports and records necessary for the evaluation and reconstruction of the clinical research study.

Government agency regulations and directives require that the study investigator must retain all study documentation pertaining to the conduct of a clinical trial. In the case of a study with a drug seeking regulatory approval and marketing, these documents shall be retained for at least two years after the last approval of marketing application in an International Conference on Harmonization (ICH) region. In all other cases, study documents should be kept on file until three years after the completion and final study report of this investigational study.

## 11.0 Data and Specimen Management

#### 11.1 Data Analysis Plan

The primary analysis will be a mixed model repeated measures ANCOVA adjusting for baseline differences in dependent measures, sex and race. Missing data will be imputed by MMRM. We would also examine some variables categorically.

Assumptions for the power analysis included random assignment into one group receiving placebo and one JNJ-18038683. The cognitive battery, as the primary instrument, will be collected at baseline and at end point (8 weeks). Using repeated measure ANCOVA, the time average difference in the response variable will be compared between groups to detect treatment difference. Based on Javitt et al, 2012, we assume the mean baseline verbal learning score will be 36.2, SD 9.4 for both groups. We are assuming the placebo group will show no improvement while the treatment group will improve a mean of 5 points, a medium effect. We assume the correlation coefficient of repeated observation to be 0.5 and the covariance structure to be compound symmetry. The power calculation was conducted with alpha level of 0.05 using one-sided and two-sided tests. Full results are available upon request. With a one sided test, 33 individuals per group are required assuming 5 points improvement of the treatment group compared to the placebo for the desired power of 80% with alpha level of 0.05. We plan to recruit 36 per group to account for drop outs. In the two sided test the sample size per group is 42.

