#### Numeric Results based on one-sided test

One-Sided Test. Null Hypothesis: D = 0. Alternative Hypothesis: D > 0 (or D < 0). Covariance Type = Compound Symmetry

Group 1	Group 2	Sample	I	Difference				
Sample	Sample	Allocation	Time	to be	Standard	Auto-		
Size	Size	Ratio	Points	Detected	Deviation	corr.		
Power(N1	) (N2)	(R)	(M)	(D1)	(Sigma)	(Rho)	Alpha	Beta
0.8023533	33	1.000	. 2	5.000	9.400	0.500	0.050	0.19765

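### Section 11.1 justifies 33 per group one-sided (36 recruited) or 42 two-sided, but the trial randomises 30 per arm: 76.9% or 66.2% power before drop-out, with sidedness undeclared

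*Protocol*

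**What the plan says.** Protocol Section 11.1 holds the only sample-size justification in either document. On sidedness it says: "The power calculation was conducted with alpha level of 0.05 using one-sided and two-sided tests". The one-sided result is "With a one sided test, 33 individuals per group are required assuming 5 points improvement", for a desired power of 80%. The recruitment target and the two-sided result follow: "We plan to recruit 36 per group to account for drop outs. In the two sided test the sample size per group is 42". The output table printed below it is the one-sided run only ("One-Sided Test. Null Hypothesis: D = 0"), with 33 per group and beta 0.19765.

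The inputs are also in Section 11.1: "we assume the mean baseline verbal learning score will be 36.2, SD 9.4 for both groups", a 5-point gain on drug against none on placebo, and "We assume the correlation coefficient of repeated observation to be 0.5 and the covariance structure to be compound symmetry". The comparison is described thus: "the time average difference in the response variable will be compared between groups to detect treatment difference".

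Everywhere else the trial is smaller. Sections 1.0, 3.0 and 4.0 set 60 patients, and Section 3.0 randomises them 1:1. Section 22.0 and the Goals section of the SAP both state 30 per arm.

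The SAP gives no sample-size calculation and no alpha. Its section on the primary efficacy analysis does not say whether the test is one- or two-sided.

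**The concern.** The justification describes a trial of 72 recruited patients (2 × 36), or 84 if two-sided (2 × 42, with no drop-out allowance). The trial being run has 60, which is fewer than the 66 (2 × 33) needed for the one-sided test with complete data. The 80% power therefore belongs to a different trial, and a reader of a null result could wrongly take it as the power of this one.

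Sidedness matters in its own right. At alpha 0.05 the critical value is 1.645 one-sided and 1.960 two-sided. A result between them is positive or negative according to a choice that neither document makes. Until that choice is fixed, the power at 30 per arm cannot be given as one figure.

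**Working it through.** **Inputs (Protocol Section 11.1):** difference 5 points; SD 9.4; correlation ρ = 0.5, compound symmetry; two time points; alpha 0.05. **Actual size:** 30 per arm (Protocol Section 22.0; SAP, Goals).

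**Effective SD.** For the average of two measurements under compound symmetry the variance factor is (1 + ρ)/2 = 0.75, so SD = 9.4 × √0.75 = 8.14.

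**Formula (normal approximation).** SE = SD × √(2/n); power = Φ(5/SE − z), with z = 1.645 one-sided or 1.960 two-sided.

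**Reproducing the plan's figures.**
- One-sided, n = 33: SE = 2.004, 5/SE = 2.495, power = Φ(0.850) = 0.8024. The printed beta of 0.19765 gives the same value. At n = 32 power is 0.7916, so 33 is the smallest adequate size.
- Two-sided, n = 42: power 0.8036. At n = 41 it is 0.7942, so 42 is also confirmed.

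**At 30 per arm, before drop-out.**
- SE = 8.14 × √(2/30) = 2.10; 5/SE = 2.379.
- One-sided: Φ(2.379 − 1.645) = 0.769.
- Two-sided: Φ(2.379 − 1.960) = 0.662.
- Noncentral t: 0.760 and 0.648.
- Difference detectable with 80% power: (1.645 + 0.842) × 2.10 = 5.23 points one-sided; (1.960 + 0.842) × 2.10 = 5.89 points two-sided.

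**With drop-out.** No rate is stated, so both rates below are assumptions. The first is inferred from 1 − 33/36 = 8.3%. Drop-outs are excluded and the formula is unchanged.

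| Drop-out | Evaluable per arm | Power, one-sided | Power, two-sided | Detectable difference (one- / two-sided) |
|---|---|---|---|---|
| none | 30 | 76.9% | 66.2% | 5.2 / 5.9 |
| 8.3% | 27.5 | 73.7% | 62.5% | 5.5 / 6.2 |
| 15% | 25.5 | 70.8% | 59.2% | 5.7 / 6.4 |

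**Carry-forward.** The SAP attaches last-value-carried-forward to its mixed model, while Section 11.1 says "Missing data will be imputed by MMRM". Whether carry-forward also applies to the SAP's ANCOVA is unclear. If it does, a simulation of 20,000 trials puts the further loss at 1.3 to 2.1 percentage points: at 8.3% drop-out, 0.719 / 0.601 with drop-outs excluded against 0.706 / 0.584 carried forward; at 15%, 0.682 / 0.561 against 0.663 / 0.540.

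**Does this carry over to the SAP's ANCOVA?** The variance factor for a baseline-adjusted Week 8 comparison is 1 − ρ², which is also 0.75 at ρ = 0.5. The two factors agree only there: at ρ = 0.4 they are 0.70 (time average) and 0.84 (ANCOVA), and at ρ = 0.6 they are 0.80 and 0.64.

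**The case against.** **The two-sided figure may be given too much weight.** Section 11.1 builds its target on the one-sided 33 and tabulates only that run. On that basis power falls from 80.2% to 76.9%, about 3 points. This is fair as to size, and the one-sided shortfall is modest. But choosing a target from one calculation does not pre-specify the primary test, particularly when the protocol reports the two-sided size beside it.

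**The shortfall depends on ρ.** For a baseline-adjusted Week 8 comparison at 30 per arm, one-sided power is 72.7% at ρ = 0.4 and 82.4% at ρ = 0.6. That stands as a qualification: the 80% is missed on the protocol's own inputs, not under every correlation.

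**The 5 points may be the wrong input for a time average.** If the arms are equal at baseline and differ by 5 at Week 8, the average over both visits differs by 2.5, and one-sided power at 30 per arm would be about 32%. This is a weakness in the protocol's description. It does not rescue the 80%, and it does not arise for a baseline-adjusted Week 8 comparison, where 5 points is the right input.

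**The SAP's primary outcome is different.** It names verbal fluency performance from four tests, whereas the power inputs are for a verbal learning score. This limits where the power figures may be quoted.

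**Other results may exist.** Section 11.1 offers full results on request, so power at other sizes may have been calculated. It is still absent from the plan.

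**Conclusion.** The concern holds and should be fixed. The current text justifies 33 evaluable and 36 recruited per group, or 42 two-sided, while the trial randomises 30 per arm. On the protocol's inputs, power before drop-out is 76.9% one-sided or 66.2% two-sided, with detectable differences of about 5.2 or 5.9 points. Drop-out lowers both figures.

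The result rests on a 5-point difference, SD 9.4, ρ = 0.5, alpha 0.05 and the normal approximation. It covers the verbal learning score only. The contradiction in sample size and the undeclared sidedness are plain from the text and depend on none of these assumptions.

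**What to change.** No added enrolment is needed.

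1. In Section 11.1, replace 36 per group with 30 per arm, and replace the 80% statement with the power and detectable difference at that size.
2. Before unblinding, declare in both the protocol and the SAP whether the primary test is one- or two-sided. In Section 11.1 quote the matching pair: about 77% and 5.2 points if one-sided, or about 66% and 5.9 points if two-sided. Say that these are before drop-out and for the verbal learning score only. The SAP needs only the sidedness sentence.
3. State that the figure assumes a baseline-adjusted Week 8 comparison, and that this matches the protocol's time-average calculation only because ρ is 0.5.

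The wider difference between the protocol's and the SAP's primary analyses is a separate matter that these edits do not settle.

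The cost is a few edits to Section 11.1, one sentence in the SAP, and a less favourable stated power. Enrolment, visits and data collection do not change.

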#### Numeric Results based on one-sided test

One-Sided Test. Null Hypothesis: D = 0. Alternative Hypothesis: D > 0 (or D < 0). Covariance Type = Compound Symmetry

Group 1	Group 2	Sample	I	Difference				
Sample	Sample	Allocation	Time	to be	Standard	Auto-		
Size	Size	Ratio	Points	Detected	Deviation	corr.		
Power(N1	) (N2)	(R)	(M)	(D1)	(Sigma)	(Rho)	Alpha	Beta
0.8023533	33	1.000	. 2	5.000	9.400	0.500	0.050	0.19765

#### 11.2 Data Management and Monitoring/Auditing

A database in the RedCap system will be used for data entry and will be formatted to simulate the hard copy data entry forms. Once entered into this database, the data files can be extracted into Excel or SAS project databases, which are maintained on a networked directory under the direct supervision of the PI and biostatistician. Back-ups are routinely performed to assure the preservation of the database. Data are checked for range, consistency, missing values, etc. During data analysis, combined datasets are created as needed. Data are maintained in the master system datasets using a source/derived data approach, where source datasets are maintained unmodified, while the derived datasets are modified as needed. Thus, alterations that prove to be incorrect are easily rectified. The confidentiality of all data is maintained using the HIPAA compliance standards of Northwestern University. No confidential information is posted to the web under

any circumstances. All possible efforts are made to retain only the necessary information in all cases.

Regarding de-identification of the data set: No identifiable information for any individuals (i.e. name, initials or date of birth) will be collected in the analyzable RedCap database or directly linked to study data. Individuals will be coded only with study-specific unique ID numbers.

# 12.0 Provisions to Monitor the Data to Ensure the Safety of Individuals

The Principal Investigator is responsible for the conduct of the clinical trial at the site in accordance with Title 21 of the Code of Federal Regulations and/or the Declaration of Helsinki. The Principal Investigator is responsible for personally overseeing the treatment of all study patients. The Principal Investigator must assure that all study site personnel, including sub-investigators and other study staff members, adhere to the study protocol and all FDA/GCP/NCI regulations and guidelines regarding clinical trials both during and after study completion.

The Principal Investigator at each institution or site will be responsible for assuring that all the required data will be collected and entered onto the Case Report Forms. Periodically, monitoring visits will be conducted and the Principal Investigator will provide access to his/her original records to permit verification of proper entry of data. At the completion of the study, all case report forms will be reviewed by the Principal Investigator and will require his/her final signature to verify the accuracy of the data.

#### 13.0 Withdrawal of Individuals\*

Individuals can be taken off the study treatment and/or study at any time at their own request, or they may be withdrawn at the discretion of the investigator for safety, behavioral or administrative reasons. The reason(s) for discontinuation will be documented and may include:

- Individual voluntarily withdraws from treatment (follow-up permitted);
- Individual withdraws consent (termination of treatment and follow-up);
- Individual is unable to comply with protocol requirements;
- Individual experiences toxicity that makes continuation in the protocol unsafe:
- Physician judges continuation on the study would not be in the patient's best interest;
- Individual becomes pregnant (pregnancy to be reported along same timelines as a serious adverse event).

#### 14.0 Risks to Individuals\*

The risks from the study procedures include:

In a 7 week, randomized, placebo controlled trial comparing JNJ-18038683 with placebo and escitalopram (an active comparator), a total of 6 serious adverse events were reported during the study (placebo group: spontaneous abortion and suicidal ideation; escitalopram group: spontaneous abortion, suicidal ideation, suicide attempt, and chest discomfort). A total of 10 individuals (3 in the placebo group, 4 in the JNJ-18038683 group, and 3 in the escitalopram group) were withdrawn from the study prematurely due to adverse events. Only 3 individuals receiving the 20-mg dose of JNJ 18038683 required dose reductions at any point during the study.

Adverse events that were reported in more than 5% of individuals in any treatment group included headache, nausea, nasopharyngitis, insomnia, somnolence, dyspepsia, dizziness, dry mouth, constipation, diarrhea, vomiting, back pain, upper respiratory tract infection, palpitations, and fatigue. The treatment-emergent adverse events that were reported more frequently in the JNJ 18038683 group compared with the placebo or escitalopram groups included dyspepsia, constipation, upper respiratory tract infection, and palpitations.

The clinical interview questions may result in temporary discomfort when asking the subject about a potentially difficult time in the past or the psychiatric symptoms they experience in the case of psychiatric participants. There may be temporary discomfort/ bruising at the site of venipuncture.

It is believed the potential benefits outweigh the risks for this trial.

In case of a medical emergency and risk of suicidality, the study team will follow the emergency protocol outlined in the Appendix 3.

## 15.0 Potential Benefits to Individuals

The possible benefits to the individuals who participate in this study are improvement in cognitive function and residual depressive symptoms, but there may be no direct benefit. Research staff could provide information from screening evaluations to the subject's clinical treatment team if requested by the subject. Findings from this study may benefit others. Participation will allow us to learn about the potential cognitive enhancing effects of JNJ-18038683 in patients with bipolar disorder, and its effect on depressive symptoms, which would inform further studies evaluating its use to treat cognitive deficits among various clinical populations.

## 16.0 Vulnerable Populations

This research study does involve cognitively impaired adults, as the primary endpoint is examining the effect of the study medication on the cognitive impairment associated with bipolar disorder (CIABP).

To ensure that each subject's rights and welfare are protected, we confirm the following:

The competency of patients to give informed consent will be evaluated in a multifaceted manner. The majority of patients who participate in our research are referred to us by clinicians. Prior to participating in any protocol-related procedures, and as per the standard operating procedure, research clinicians explain the nature of the protocol to the patient, the risks and benefits, and the option not to participate in research. They have been instructed by us not to refer patients they believe are incompetent or grossly disorganized. This process of assessment and explanation is then repeated by the clinician involved in the research project, often in the presence of clinical staff, and by the research assistant involved in the research project. They first do a clinical assessment to determine if the patient might be appropriate for the project in terms of its inclusion and exclusion provisions. During this clinical assessment, they do a mental status examination, which assesses the patient's memory, attention, and thinking processes. If these are impaired to the point where the person appears to be unable to understand the nature of the research project, its risks and benefits, or the option not to participate, they will not be approached to be in research. If they are not excluded for this or other reasons, e.g. patient is a risk to themselves or others, one of the subinvestigators on the study or the PI will explain the protocol, go carefully over the consent form, provide help to the patient, if needed, to review the written protocol and consent, ask question to the patient to determine their level of comprehension, and then answer all questions the patient may have about the study. This will often be done in the presence of a clinical staff member not directly connected to the research or minimally involved. This type of assessment is repeated as needed during the course of the protocol if there is a question about loss of competency, although it is expected that competency will increase rather than decrease because of the beneficial effects of the treatments. Where the research staff feels the decision as to competency is questionable, the patient will be excluded from research. In a few cases, we may ask a clinician not connected to the research to do an independent evaluation their decision will be decisive.

Individuals will be regularly evaluated for the increase of cognitive deficits. If and when increased cognitive deficits emerge, the P.I. or sub-investigator will assess for any impairments in judgment that might affect the subject's ability to judge if he or she should continue to participate. If there are any conflicts about the impairment of a given patient, the P.I, [name], will request [name], Chairman of the Feinberg School of Medicine Department of Psychiatry, to evaluate the patient. [name] will then independently determine if he believes that the patient is continuing to give consent and if continued participation is in the patient's best interest. If [name] determines that the patient has withdrawn consent or that continuing is not in his or her best interest, the subject will be withdrawn from continued participation and referred for appropriate follow-up treatment. If and when increased cognitive deficits emerge in a subject at the Beacon Medical Group Behavioral Health

South Bend site, the same process will take place as at the Northwestern University. If there are any conflicts about the impairment of a given patient, the P.I will ask an independent psychiatrist from the Beacon Medical Group Behavioral Health South Bend, South Bend, IN to evaluate the patient. This psychiatrist will then independently determine if he/she believes that the patient is continuing to give consent and if continued participation is in the patient's best interest.

The risk of the study is low, and are reasonable in relation to the potential benefits. Individuals cannot access alternative pharmacologic treatment for CIABP, as there is no approved treatment.

